# THO 1524: [F]FSPG PET Protocol

relevant information available in the patients' medical records. The final PET/CT interpretations (F-FSPG; F-FDG PET/CT, clinical CTs and other relevant clinical imaging available for comparison) will then be compared to determine the impact of F-FSPG PET/CT on the final diagnosis, and specifically to determine if the F-FSPG PET/CT would have changed the diagnosis and/or stage of disease compared to the clinical SOC CT and/or F-FDG PET/CT. These results will be reported to the biostatistician who will compile the data for estimation for analysis (*see* Statistical Consideration Section).

At this time, the investigational data will not be used to direct care (e.g. influence treatment decisions) until we have sufficient knowledge of the usefulness of the data in this regard compared to standard of care procedures.

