Final diagnosis will be based on tissue biopsy (surgical or *via* a high-quality core biopsy) or negative (no growth) two-year follow-up with CT. We will assign patients with IPNs into the

"benign" category if their IPNs remain stable for two or more years, decrease in size, or resolve during CT follow-up, performed in accordance with Fleischner Society guidelines.

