# Imaging Protocol: F-FSPG (Figure 1)

[figure not shown]
Each patient will undergo an SOC whole-body (vertex to mid thighs) F-FDG PET/CT scan within 60 working days of an F-FSPG PET/CT scan for these first 60 enrollees, with no intervening cancer treatment of the target lesion (limited biopsies or resections are allowed). A minimum of 12 hours must lapse between SOC (F-FDG) and F-FSPG PET/CT scans. Standard of care procedures performed prior to consent but within the protocol defined windows for each

assessment can be used for study purposes. All research only procedures must be performed after the consent date.

Eight (8) subjects with either indeterminate nodule(s) or thought or known to have newly diagnosed lung cancer, will receive an F-FSPG PET scan (emission only), acquired dynamically after injection over the nodule/mass of interest for 60 minutes, in order to characterize the time activity curves of F-FSPG. These 8 subjects will then have a short break (bathroom, stand up) and then receive a PET/CT scan from the vertex to the mid-thighs. This final body PET/CT covers the same anatomic range as the SOC F-FDG PET/CT, and will be compared closely to the F-FDG PET/CT to determine if there is added value of the F-FSPG PET/CT. Once the dynamic PET/CT scans with F-FSPG in the initial 8 subjects are obtained, the remainder of subjects will have a scanning protocol from vertex to mid-thighs about 60 minutes after F-FSPG injection, similar to the protocol for standard of care F-FDG PET/CT.

The third year will be used, if needed, to obtain at least two years of CT follow-up for patients with IPNs who chose serial follow-up CT scans over a tissue diagnosis (two years is required by Fleischner Society Guidelines to prove stability/benignity for solid nodules), though over 90% of malignant IPNs will demonstrate growth within one year by CT.

Figure 1: Flow Schema of Imaging:

\*Optional tissues collection noted in Figure 1 are part of separately enrolled study and not called for on this protocol.

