#### **11. Statistical Considerations**

#### **Study Design**

As we have shown from a large review of patients referred to us for IPNs and lung masses, F-FDG PET/CT has 92% sensitivity but 40% specificity for diagnosis of cancer, primarily due to inflammatory (especially granulomatous) lung nodules in our population. For F-FSPG to have a significant impact, we assume that the sensitivity of F-FSPG will be equal to F-FDG, but that the specificity of F-FSPG for the diagnosis of lung cancer will be 80%. Given the preliminary data we have shown with virtually no F-FSPG uptake in an active granulomatous abscess, we are very optimistic that our approach could succeed.

Our preliminary proposed investigation will include 30 subjects who had both PET scans done FDG and FSPG of patients meeting enrollment criteria and referred from the VUMC Pulmonary Medicine or Thoracic Surgical Oncology services. We will include those IPNs or lung cancers discovered *via* lung cancer screening or referred for a non-screened discovered IPN or cancer. If our preliminary data are encouraging, we will seek additional funding to enroll more to achieve statistical significance. However, we predict that we will need to extend the study to a total of 70 subjects completing a study to achieve significance. Our plans for the additional funding will be to approach the current IP holder (Piramal Life Sciences) as well as to apply for extra-mural funding with initial data from our initial subjects.

**Go/No-Go criteria:** To verify that data collected in this pilot imaging study supports proceeding to a larger efficacy trial, clear Go/No-Go criteria, which will be assessed at the end of enrollment and data analysis, have been established for each aim, and include:

A. Aim  $1 - {}^{18}$ F-FSPG PET/CT has equal sensitivity to  ${}^{18}$ -FDG PET/CT, with  $\ge 50\%$  specificity, compared to the proven 40% specificity of  ${}^{18}$ F-FDG PET/CT, for the diagnosis of indeterminate lung nodules, in our area with high endemic rates of fungal nodules.

B. Aim 2 –  $^{18}$ F-FSPG PET/CT is at least equivalent in overall accuracy to  $^{18}$ F-FDG PET/CT for staging of lung cancer.

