# Primary Endpoints: Results from F-FSPG PET/CT:

- Demonstrate significance accuracy in discrimination of benign from malignant nodules/masses equal to or greater than F-FDG PET/CT, especially for inflammatory/infectious lung nodules, or trend toward significance should additional subjects be enrolled.
- 2. Demonstrate equivalent or superior accuracy for staging of lung cancer compared to F-FDG PET/CT, or trend towards significance should additional subjects be enrolled.

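### Staging accuracy is a primary endpoint, but no reference standard for stage is defined, and a count of stage changes cannot show which tracer was right

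*Combined protocol and SAP*

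**What the plan says.** **The claim.** In Section 11, Primary Endpoints, the second endpoint is to "Demonstrate equivalent or superior accuracy for staging of lung cancer compared to" FDG PET/CT, or to show a trend if more subjects are enrolled. Under Go/No-Go criteria in the same section, criterion B is met if FSPG "PET/CT is at least equivalent in overall accuracy to" FDG PET/CT for staging. Section 2 (Specific Aim 2) goes further and asks whether FSPG is superior for baseline diagnosis and staging.

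**The reference standard.** Section 5 states: "Final diagnosis will be based on tissue biopsy", surgical or by "high-quality core biopsy) or negative (no growth) two-year follow-up with CT". Its use there is to settle whether a nodule is benign. Section 5 also plans to correlate FSPG findings with FDG and with surgical pathology in patients who have tissue. It does not mention nodal or distant stage.

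**The staging comparison.** Section 7, Clinical Data Analysis, says that the final interpretations "will then be compared to determine the impact of" FSPG on the final diagnosis, and specifically whether FSPG "PET/CT would have changed the diagnosis and/or stage of disease compared to the clinical SOC CT and/or" FDG PET/CT. Those results go to the biostatistician. Readers have the conventional imaging and the medical record. FSPG results are not to direct care.

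**The analysis.** Section 11, Data Analysis, lists sensitivity, specificity, overall accuracy and ROC curves for both tracers and places Aim 2 in known or confirmed lung cancers. For stage it gives no truth, unit of analysis, margin or test.

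**The concern.** Accuracy is agreement with the truth. To compare the staging accuracy of two tracers, each patient (or nodal station, or distant site) needs a reference stage, and each tracer's stage must be scored against it. The plan supplies a truth for the lung lesion and none for the stage. What it supplies for stage is a comparison of FSPG with standard-of-care CT and/or FDG, which measures disagreement between methods.

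Verification is also uneven. Because FSPG does not direct care, a node or distant site seen only on FSPG may never be checked, while the clinical work-up can use FDG.

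At stake is one of two primary endpoints and one of three Go criteria. Section 7 also allows statistical superiority in diagnosis and/or lung cancer evaluation to start a larger trial of 40 additional subjects.

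**Working it through.** The documents give no sample size, power, margin or expected accuracy for staging, so there is no staging figure to reproduce. The check has three steps.

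**1. Does any section define true stage?**

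| Place | What it settles | Truth for stage? |
|---|---|---|
| Section 5, final diagnosis | Benign or malignant lesion | No |
| Section 5, surgical pathology correlation | FSPG against FDG and pathology, in patients with tissue | Stage not named |
| Section 7, Clinical Data Analysis | Whether FSPG would alter the stage from standard-of-care CT and/or FDG | No, measures change |
| Section 11, Data Analysis | Overall accuracy of both tracers | Truth for stage not stated |
| Section 13, calendar | Chest CT over two years, required only without a biopsy diagnosis | No |

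**2. What can a change count show?** Among patients with cancer, let

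- b = share staged correctly by FSPG only,
- c = share staged correctly by FDG only,
- d = share in whom the FSPG stage differs from the FDG stage.

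The accuracy difference (FSPG minus FDG) is b - c. Where the two stages agree, both are right or both are wrong, so these patients contribute nothing. Where they differ, at most one is right, so b + c ≤ d. Hence

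-d ≤ b - c ≤ +d.

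The count yields d and says nothing about the sign of b - c. The documents give no value for d, so these are assumptions:

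| Assumed d | Possible accuracy difference |
|---|---|
| 10% | -10 to +10 points |
| 20% | -20 to +20 points |
| 30% | -30 to +30 points |

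With the 28 cancers that Section 11 expects among 70 completers, d = 20% means 28 × 0.2 = 5.6 changed stages, and nothing recorded says which were improvements. The bound assumes that the comparator stage is the FDG stage. The and/or wording also admits CT alone, in which case the count does not bound the FSPG minus FDG difference at all.

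**3. What would an independent reference give?** It makes b and c observable. Power of the exact McNemar test, two-sided 5%, is the sum over m discordant pairs of P(m; n, b + c) × P(reject | m), with the pairs favouring FSPG distributed Bin(m, b/(b + c)). All discordances are assumed, with c = 0.05:

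| b | Difference | Power, n = 28 | Power, n = 12 |
|---|---|---|---|
| 0.15 | 10 points | 8.5% | 0.3% |
| 0.20 | 15 points | 20.8% | 1.4% |
| 0.25 | 20 points | 36.5% | 3.7% |
| 0.30 | 25 points | 52.8% | 8.0% |

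Here n = 12 is 30 × 0.4, the initial 30 subjects at the stated 40% prevalence. The entry criteria also admit newly diagnosed cancers, so the true number could be higher. These powers suppose that every cancer has the reference; fewer will.

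**The case against.** The best defence is that the protocol never says the change count is the accuracy analysis. Section 7 describes an impact measure, Section 11 separately promises overall accuracy for both tracers, and Section 5 plans a correlation with surgical pathology. That stands in part: pathology will exist for some patients and the protocol intends to use it. It does not close the gap, because neither Section 5 nor Section 11 says what true stage is.

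A reader might infer something stronger: that the FDG-informed clinical stage is the truth, so FDG is right by construction, every disagreement counts against FSPG, and FSPG cannot be shown superior. If that stage were the reference, FDG would score 100% and FSPG 1 - d, and superiority would indeed be impossible. The documents state no such rule. Section 7 frames a difference as impact, and its Imaging Protocol compares the scans closely with FDG "PET/CT to determine if there is added value of the" FSPG scan. Standard care also includes CT and clinically indicated biopsy, so the clinical stage is not simply the FDG stage. The direction is undefined, not fixed against FSPG.

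It is also fair that the study is presented as preliminary, and that Section 11 ties its explicit Go and No-Go consequences to Aim 1. This limits the damage but leaves a primary endpoint without a means of evaluation.

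**Conclusion.** The concern holds in this form: as written, the plan cannot determine whether FSPG stages lung cancer better than, as well as, or worse than FDG. The described output leaves the accuracy difference anywhere between -d and +d. The 20-point figure is an illustration, because d is assumed; the conclusion does not depend on its value so long as some stages differ. The result rests on two readings: that Section 5's reference standard covers lesion diagnosis only, and that no other section defines stage truth. Sites seen only on FSPG may also go unverified, but no size for that effect can be derived from the documents. The change should be made before analysis. It does not undermine Aim 1, which has its own reference standard.

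**What to change.** Amend Section 11, and Section 7, Clinical Data Analysis, as follows.

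- Record the FDG stage and the FSPG stage separately, and score each against one reference that excludes both PET reads: pathological stage at resection, nodal sampling, or biopsy of a distant site, wherever these were done clinically.
- Limit endpoint 2 and Go criterion B to patients or stations with that reference, and state which of the two is the unit of analysis.
- Compare the tracers by a paired analysis of the signed discordances (b against c). A claim of equivalence also needs a prespecified margin, which the plan lacks for staging.
- Use follow-up imaging as a reference only where it is already in the record and can be interpreted despite treatment. It cannot be the general fallback: by the Section 13 calendar, biopsy-proven cancers have no protocol-required follow-up CT, and the calendar lists chest CT only, whereas the PET scans run from vertex to mid-thighs.
- Report all other discordant sites as unresolved, and note that the choice of verified sites may itself be FDG-informed.
- Keep the change-of-stage result as a descriptive measure of impact, not as accuracy.

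The cost is a wording change and abstraction of pathology and any usable imaging from the record, with no new procedure for patients. Fewer patients will count towards the staging result and its precision will fall. The endpoint becomes estimable, but as the power figures show, it is not powered for superiority and should be reported as an estimate with its confidence interval.

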#### **Rationale for Size Criteria**

The rationale of a minimum diameter of 7 mm for IPNs and lung cancer for our investigation is based on the usual lower limit of detectability on PET imaging. While this is usually reported as 8-10 mm in the literature, much of this is based on older technology PET scanners. The size of 7 mm is also the minimum size in which evaluation of an IPN becomes technically feasible (11, 38) in terms of:

- 1) Number of patients to manage
- 2) Limited clinical means by which to obtain tissue diagnosis of such a small IPN
- 3) Risks/benefits of definitive evaluation of a nodule this small

While overall very safe, definitive evaluation of such small IPNs often requires a core biopsy via a transthoracic or transbronchoscopic biopsy, VATS wedge resection or even an open thoracotomy since fine-needle biopsies are often non-definitive. Given the co-morbidities frequently present in patients at high risk for lung cancer, the perioperative mortality is likely to be 1.0%. Since the majority of IPNs, even in high-risk patients, are benign, we must choose a minimum size threshold at which the potential benefits for the patient justify the pain, cost and risk of a definitive answer.

Henschke *et al.* (39) recently addressed this in a retrospective review of 21,136 subjects enrolled in a low-dose CT lung cancer screening program performed between 2006–2010, in which malignancy rates of various size ranges of IPNs were evaluated. With a cut-off of 7 mm in diameter for IPNs, instead of 5 mm, was used, the percentage of patients with a "positive" screening CT at baseline for an IPN decreased from 16% (5 mm threshold) to 7.1% (7 mm threshold). When these patients were then evaluated for subsequent diagnosis, a delay in diagnosis of lung cancer by 9 months occurred in about 5% of patients using the threshold of 7 mm diameter as the minimum size for close interval follow-up, while the percent of "positive" screening exams decreased by over half (**Table 1**). Accordingly, though still debated, the definition of a "positive" CT screening examination for lung cancer will likely need to address practical, realistic management issues that will include the size of the IPNs to be definitively evaluated *versus* followed, particularly given the low but real morbidity/mortality associated with invasive procedures when the vast majority of even high-risk patients will have a benign IPN. Given these practical management results and the limits of resolution of current PET scanners, we have chosen the lower limit of size for our investigation of IPNs or lung cancer to be 7 mm.

Table 1\*

IPN diameter (mm) defining a "positive" CT	5	6	7	8	9
Total percent of patients "positive" on CT	16%	10.2%	7.1%	5.1%	4.0%
Patients (%) meeting diameter threshold with delay in cancer diagnosis of 9 months	0%	0%	5.0%	5.9%	6.7%

\*Henschke et al. (39)

# Pathology Methods

 $x_c$  and CD44: To examine the correlation of accumulation of F-FSPG PET with  $x_c$  and CD44 in lung tumors, tissues specimens from fine-needle biopsies obtained from routine pathologic examinations will be obtained before or after PET/CT imaging for immunohistochemistry (IHC) and Western blotting (WB) studies. For patients having surgical excision/biopsy after F-FSPG PET/CT, this tumor specimen will be used for further pathologic examination. Tissue processing and IHC analysis of formalin-fixed, paraffin-embedded tissue sections will be performed as detailed in our previous publications (40, 41). Briefly, 4-Im thick whole tissue sections were transferred onto poly-L-lysine-coated adhesive slides and dried at 74 °C for 30 minutes. After standard heat epitope retrieval for 1 hour in EDTA, pH 8.0, in the autostainer, the samples were incubated with antibodies for targeted epitopes. The level of expression of our proteins in both membrane and cytoplasm and in the membrane of malignant tumor cells will be examined by an experienced pathologist who is completely blinded to any patient and imaging information. The numerical results of the IHC will be semiqualitatively evaluated using a scale of 0, 1+ (weak), 2+ (medium), and 3+ (strong) with a sample being reported as positive if greater than 10% of the cells in the sample were positively stained. The correlation between the intensity of IHC staining and SUVmax of the corresponding lesion on the PET/CT will be assessed. This processing approach will allow for comparison of definite pathology and tracer imaging findings.

TMAs: Tumor and benign specimens will be assembled in Tissue Microarrays (TMAs) with associated clinical information. All TMAs will be paraffin-embedded blocks formed from cores derived from multiple paraffin-embedded tissue blocks, containing hundreds of cases in a single accessible block, fully annotated with clinical data elements covering patient demographics, past medical history, smoking history, details about the tumor diagnosis, stage, histology, imaging, and follow-up. TMA construction begins with a detailed plan and approval by the VUMC IRB and the VICC Lung SPORE PTIC Tissue Utilization Committee with successful data sharing agreements and off-site tissue banking waivers successful in the past. Slides corresponding to the tissue blocks of interest are reviewed by pathologist ([name]) director for tumor identification and marking, and the block construction (Beecher Instruments, USA) is completed. To date, we have 26 lungspecific TMAs containing samples from approximately 750 patients with associated clinical data and including a variety of tumor types.

Immunohistochemistry (IHC): TMA tissue sections are evaluated for intensity and distribution of IHC staining. Scoring is performed by one or more pathologists, including the core

Tissue Biorepository director, [name]. The scoring system routinely used for evaluation of IHC staining is an index based on intensity and percent tumor positivity modeled after methods we have used extensively in the past (40). In addition to the intensity and estimate of percent positive tumor cells, the cellular localization of staining is documented (nuclear, cytoplasmic, or membrane).

#### 8. Risks

#### Radiopharmaceutical

The radiopharmaceutical (F-FSPG) used in this study for PET scanning has been evaluated in humans previously (31, 35). No adverse side effects such as anaphylactic reactions, allergic reactions, or mortality or morbidity have been reported to the best of our knowledge. For a complete safety listing of F-FSPG, please refer to the Investigational Brochure (IB) of Piramalheld IND 121728. The total mass of radiopharmaceuticals administered in this study is in the subpharmacological amount (<100 micrograms), and thus is expected to have no physiologic effect on the patient or tumor. F-FSPG is produced by the Vanderbilt Radiochemistry Core Laboratory according the CMC section of Vanderbilt-held IND 124202 ([name] [name], PI) and meets all USP <823> requirements for a sterile, injectable PET radiopharmaceutical.

#### Injection

Risks and side effects related to the IV catheter may include discomforting pain at the site of injection, bleeding, and bruising.

# **Reproductive Risk**

Patients should not be pregnant while on this study because the imaging agent being tested contains a small amount of radioactivity. This could affect an unborn baby. Female subjects of childbearing potential must have a negative serum or urinary pregnancy test within 24 hours of the proposed investigational PET/CT scan prior to injection of the investigational radiopharmaceutical in accordance with the policies of the Vanderbilt University Medical Center IRB and Department of Radiology.

#### **Dose Rationale**

A dose of 300 MBq (8.1 mCi) for F-FSPG studies was chosen in accordance with a typical radioactive dose of F-FDG used for oncological diagnostics (350 MBq for an adult). This dose is expected to provide suitable imaging contrast of the target structures.

# **Radiation Safety**

Effective radiation doses for F-FSPG were calculated from biodistribution studies in mice and were determined in five healthy volunteers. Extrapolated effective doses from mice are 5.10 mSv for a male and 6.54 mSv for a female subject, assuming a patient dose of 300 MBq and a bladder-voiding interval of 45 min. In humans, an effective dose of 4.5 mSv was determined in healthy volunteers from an injection of 300 MBq/8.1 mCi of F-FSPG.

# **Toxicity Studies**

The tracer (F-FSPG) used in the study has been evaluated in humans previously without incident (31, 35). The evaluation of the toxicity of FSPG included an extended single-dose toxicity study in rats and in dogs and the evaluation of the genotoxic potential in a gene mutation assay (Ames test) and an assay on clastogenic effects (micronucleus assay *in vitro*). For a complete description of F-FSPG toxicity, please refer to the Investigational Brochure (IB) of Piramal-held IND 121728. Additionally, the effects of the impurities of the anticipated clinical kit formulation were evaluated in an extended single dose toxicity study over three days in rats with a decayed kit-formulation. All toxicological studies were performed according to GLP principles. Since these studies were intended to evaluate the chemical toxicity of FSPG and not the potential effects of the radiation, the non-radioactive F-labeled analogue was used for toxicological testing.

